13.2.2 Reporting of Serious Adverse Events (SAE)

The investigator is responsible for notifying the sponsor via Axonal-Biostatem **without delay from the day** he/she becomes aware of all serious events related to the DM occurring during the research.

In the event of an SAE, the investigator must complete the specific form for SAEs provided by the Sponsor. Any SAE related to the DM must nevertheless also be reported on the eCRF pages intended for the collection of vigilance.

As soon as the investigator is aware of the occurrence of an ADR related to the DM, he/she must **immediately notify the Sponsor, or its representatives, and the CRO in charge of the study logistics** (Axonal-Biostatem) by e-mail within **24 hours of becoming aware of the event**, by sending the completed ADR form to :

Vigilance correspondent :

Responsible for the vigilance service :

[name]

VIGIPHARM

[name]

[name]

Tel: [name]- [contact]

[contact]

This SAE form must be completed and submitted for all SAEs, regardless of a possible causal relationship. This form is also available in the eCRF.

The investigator is asked to document in detail in the SAE report the course of the AE, as well as any treatment administered and any relevant data. The investigator will be asked to comment on the causality of the event in relation to the research on the SAE form.

The investigator should follow the SAE until it is resolved and inform the Sponsor of any new follow-up information and the progress of the SAE (follow-up report).

In the case of death, the investigator is requested to send the Sponsor any available additional information (e.g. autopsy report, medical report).

The CRO will immediately inform the study's vigilance correspondent (VIGIPHARM) by sending them the SAE form and ensuring that it is correctly transmitted.

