3.3 EXPECTED SERIOUS ADVERSE EVENTS

As with any Class IIB medical device, risks associated with use cannot be excluded.

Each patient will already be using an Omnipod® insulin pump at the time of inclusion in the study. The use of another pump model (CE marked and already used in other countries) does not present any additional potential risk.

Any serious adverse event, whether or not related to the device under study or its use, must be reported in accordance with the instructions in Chapter 13.

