13.2 INVESTIGATOR'S RESPONSIBILITIES

13.2.1 Notification of adverse events (AEs)

Patients will be encouraged to report any DM-related incidents and DM-related tolerance incidents to the investigator.

At each assessment, the investigator will interview the patient to determine if any adverse events have occurred.

The physician will report in the eCRF all DM-related incidents and DM-related tolerance incidents observed or spontaneously reported by the patient throughout the study (as soon as the patient's signed consent to participate in the study is obtained).

AEs not related to the DM or not related to the procedure for implanting the DM will not be reported in the eCRF. However, physicians must report any adverse reaction suspected to be due to a drug or product by mail to the regional pharmacovigilance center (CRPV) on which they depend or on the website <http://solidarites-sante.gouv.fr/soins-et-maladies/signalement-sante-gouv-fr>.

DM-related incidents and DM-related tolerance incidents will be documented in detail in the observation book (eCRF). The following information should be filled in:

- Date and time of AR onset,
- Duration of AE (indicating the total duration of the AE or symptom or determining this duration from the start and end dates and times of the evolution),
- Intensity of AE (mild, moderate, severe),
- The causal relationship of the AR to the DM AND/OR to the procedure related to the DM,
- Any action taken with respect to the product under investigation and to address this AR,
- Evolution of the AR (e.g. complete resolution, persistence...),

The investigator should assess the intensity, severity and causality of all adverse events.

These should be followed up until the event is resolved.

Determination of duration:

If the total duration of the AR or symptom is not directly indicated, it will be calculated from its onset and end dates.

Intensity Assessment :

The investigator will specify the intensity of the AE according to the following classification: mild, moderate, severe taking into account the possible degrees of intensity of the event according to the following definitions:

Slight	
 ▪ Causes mild or transient discomfort, not requiring intervention or treatment. ▪ Does not limit or interfere with daily activities.
Moderate	
 ▪ Causes enough discomfort to limit or interfere with daily activities. ▪ May require treatment.

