13.4 SUPERVISORY COMMITTEE

All incidents involving the medical device will be collected during the study and evaluated by a Monitoring Committee.

This Supervisory Committee will consist of 3 independent members.

Each member will be required to sign an attestation of no potential pecuniary conflict of interest related to the study results, and should not be known to have a "strong opinion" on the relative merits of the interventions tested in the study.

This Committee will meet at the request of the Scientific Committee, the Sponsor or the investigators.

He will be responsible for:

- Conduct regular reviews of the safety and performance elements of the study to ensure the safety of participants and that the benefit/risk ratio remains favorable for continuation of the trial
- Monitor medical or scientific information made public that may have an impact on the study in progress and the safety of participants
- Carry out the adjudication of the SAEs to decide on the imputability or not of the medical device and/or the procedure of use
- Write recommendations on continuation, modification or discontinuation of the study to the Scientific Committee and the Sponsor, based on the criteria below.

A study termination is considered if:

- The data show a statistically significant increase in the risk of adverse events making the benefit/risk ratio unacceptable,
- A serious and unexpected risk is detected,
- The state of the art makes the studied technology obsolete.

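### Protocol 13.2.2 ties the notification deadlines and eCRF entry to device-related SAEs while also requiring all SAEs, so an SAE judged unrelated has no deadline and no stated route into the safety tables

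*Protocol*

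**What the plan says.** Two rules stand side by side in the protocol.

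**All SAEs.** Section 3.3 states: "Any serious adverse event, whether or not related to the device under study or its use, must be reported", and refers to Chapter 13 for how. Section 13.2.2 has "In the event of an SAE, the investigator must complete the specific form for SAEs provided by the Sponsor" and, further on, "This SAE form must be completed and submitted for all SAEs, regardless of a possible causal relationship".

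**Device-related events only.** The opening sentence of 13.2.2 requires notification without delay from the day "he/she becomes aware of all serious events related to the DM occurring during the research". The 24-hour e-mail duty in the same section begins: "As soon as the investigator is aware of the occurrence of an ADR related to the DM". The sentence in 13.2.2 on the eCRF vigilance pages names only SAEs related to the device. Section 13.2.1 adds: "AEs not related to the DM or not related to the procedure for implanting the DM will not be reported in the eCRF". It makes no exception for serious events.

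**Downstream.** The opening of section 13 gives the CRO the task of collecting device-related incidents and device-related tolerance problems. Section 13.4 describes what is collected for the committee as device incidents, but also gives it this duty: "Carry out the adjudication of the SAEs to decide on the imputability or not of the medical device". SAP 7.5 codes device-related incidents and tolerance in MedDRA, and draws its individual listing from the adverse event data in the eCRF.

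**The concern.** Relatedness is meant to be decided by people other than the treating investigator: under 13.2.1 the sponsor rules on causality, and under 13.4 the committee adjudicates SAEs. Both tasks need SAEs that have not already been sorted by relatedness. In 13.2.2 the sorting comes first. It is done locally, in an open-label trial, by someone who knows which pump the patient wears.

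Two things are at stake. The first is oversight: an SAE judged unrelated may arrive late, or may not be put before the committee. The second is comparability of the arms: a safety table limited to events called device-related depends on an unblinded judgement, and on which sentence of 13.2.2 each centre followed. One of the committee's grounds for considering termination is an increased risk of adverse events, and judging that also needs like-for-like capture in the two arms.

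**Working it through.** No arithmetic applies. The claim rests on no rate, margin or sample size, and the documents give neither an SAE rate nor the share of SAEs judged unrelated. The check is to follow one SAE that the investigator judges unrelated through each step, on the reading most favourable to the plan: the form for all SAEs, with the clock and the eCRF pages for related ones.

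1. **SAE form.** Required by both all-SAE sentences in 13.2.2 and by 3.3. The CRO then forwards the form at once to the vigilance correspondent. On this reading the event does reach the sponsor's side.
2. **Deadline.** Both time limits in 13.2.2 are triggered by device-related events. The sentence requiring the form for all SAEs carries no time limit. Section 12 has the CRA verify that SAEs are reported on time, but no time is set for this event.
3. **eCRF vigilance pages.** 13.2.2 names only device-related SAEs for these pages, and 13.2.1 excludes unrelated adverse events from the eCRF. 13.2.2 also says that the SAE form can be found in the eCRF. That does not require an entry on the vigilance pages, and it does not settle the conflict with 13.2.1.
4. **Safety tables.** SAP 7.5 announces coding only for device-related incidents and tolerance, and its listing uses what the eCRF holds. Its yes/no item for other adverse events lists events linked to tolerance, so it does not clearly cover an unrelated SAE. No sentence brings such an event into a table, even when its form has been submitted.
5. **Committee.** The described intake in 13.4 is device incidents. The adjudication duty speaks of SAEs without a relatedness filter. The section does not say whether SAE forms for unrelated events are passed on.

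On the less favourable reading, where the opening sentence of 13.2.2 governs, step 1 is in doubt as well.

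The gap is therefore firm for the deadline, the vigilance pages and the tables. It is conditional for the committee, and conditional for the sponsor only on the stricter reading.

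**The case against.** The case for the plan is substantial. The all-SAE sentence is explicit, the form goes on to the vigilance correspondent, and it asks for the investigator's view on causality, so relatedness is already recorded there. The opening of section 13 gives the sponsor the reconciliation of the vigilance and clinical databases, and refers to a Safety Management Plan that is not among the documents. The exclusion of unrelated events from the eCRF is applied consistently in section 13, 13.2.1, 13.2.2 and SAP 7.5, so it can be read as a choice of scope.

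These points rule out several stronger conclusions that a reader might draw:

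- **That an SAE called unrelated never reaches adjudication.** The form is required for it, and 13.4 does not limit adjudication to related SAEs. It may fail to reach the committee; the text does not say that it must.
- **That it leaves no trace in the eCRF.** The form is available there. What is missing is a required entry on the vigilance pages.
- **That severe hypoglycaemia put down to patient behaviour would be lost.** Section 13.1 counts use error and misuse as device effects, and 13.2.1 reserves the unrelated category for events clearly due to other causes. Level 3 hypoglycaemia is also a secondary endpoint (10.2).
- **That each SAE lost or delayed moves an arm's rate by 2 percentage points.** That is only 1/50, from the 100 patients in SAP 5.1 split 1:1. A delayed SAE changes no rate, and nothing shows that any SAE was lost.

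What the objection does not remove is the missing deadline, the conflicting triggers within 13.2.2, and the absence of unrelated SAEs from the SAP tables. Reconciling two databases does not put an event into a table that the SAP does not define.

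**Conclusion.** The inconsistency is on the page and should be resolved. An SAE judged unrelated has to be reported, but the plan states no deadline for it, requires no entry on the eCRF vigilance pages and gives it no route into the safety tables; whether it reaches the committee is unclear. This is a defect of reporting rules and analysis scope. It is not evidence that events went missing.

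Its size cannot be given: the documents contain no SAE count and do not say how centres applied the rule. The conclusion assumes that the Safety Management Plan does not already settle the matter. Even if it does, the protocol and SAP should agree with it.

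**What to change.** **Protocol.** Reconcile 3.3, the opening of section 13, 13.2.1, 13.2.2 and 13.4 so that every SAE in both arms, from consent to the last visit and including the V3 to V4 month, is notified under one stated deadline (the 24 hours already in 13.2.2) and recorded in the eCRF. Keep relatedness to device and to procedure as recorded fields that the committee adjudicates, and state that all SAEs go to the committee.

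**SAP 7.5.** Add a table of all SAEs by arm regardless of relatedness. Show the V3 to V4 month separately, because Omnipod-arm patients may then be using the Medtrum pump. This step is needed in its own right: rewording Chapter 13 alone would leave unrelated SAEs outside the coded tables.

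**Patients already followed.** SAP 5.1 reports that 100 patients were included, so new wording cannot change notifications already made. For these patients, reconcile the SAE forms and the vigilance database with the clinical database, a task section 13 already gives the sponsor, and report which rule each centre applied.

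**Cost.** Wording changes in both documents, an eCRF instruction, a small number of extra entries, one extra table and the reconciliation work already assigned.

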13.2.3 Pregnancy Notification

The investigator must also notify the CRO vigilance correspondent (Axonal-Biostatem) of any case of pregnancy.

The CRO will immediately inform the study's vigilance correspondent (VIGIPHARM) by sending them the form for declaring grossness, and ensuring that it is correctly transmitted.

In case of notification of pregnancy, a follow-up of the AR will be done until 3 months after the birth of the child. Furthermore, if the birth is scheduled after the basic freeze, the information received will be processed afterwards.

13.2.4 Notification of overdose

The investigator must also notify the CRO vigilance correspondent (Axonal-Biostatem) of any case of drug overdose.

13.2.5 Notification of New Facts

Any development that may be sufficient to consider changes in the use of the medical device being tested, in the conduct of the research, or in the research documentation, or that may lead to a reassessment of the benefits and risks of the research, should be reported to the sponsor **without delay** by the investigator.

13.2.6 Notification of vigilance incidents

All vigilance incidents must be reported by the investigator after having been informed by e-mail to the Sponsor, or to its representatives and to the CRO in charge of the study logistics (Axonal-Biostatem), by sending the duly completed vigilance form.

Vigilance correspondent :

Responsible for the vigilance service :

[name]

VIGIPHARM

[name]

[name]

Tel: [name]- [contact]

[contact]

Notification without delay

Notification of incidents or risks of serious incidents involving a medical device that have resulted or may result in the death or serious deterioration of the state of health of a patient must be made without delay:

- Death of the patient or threat to life,
- Permanent or significant disability or incapacity,
- Need for hospitalization or prolongation of hospitalization,
- Any circumstance requiring medical or surgical intervention
- Occurrence of a congenital anomaly or malformation.

Other incidents

All of the following other incidents should also be reported by the investigator:

- Any malfunction or alteration in the characteristics or performance of the medical device,
- Any harmful and unintended reaction that occurs when the medical device is used for its intended purpose,
- Any harmful and unintended reaction resulting from the use of a medical device not in accordance with the manufacturer's instructions.

13.3 SPONSOR'S RESPONSIBILITIES

The Sponsor is responsible for the ongoing evaluation of the safety of the research and for reporting vigilance information to the appropriate regulatory authorities.

The sponsor will transmit to all concerned investigators via Axonal-Biostatem information that may affect the safety of the persons involved in the research, including any relevant

information regarding suspected ADRs related to the DM or any significant safety-related event.

13.4 SUPERVISORY COMMITTEE

All incidents involving the medical device will be collected during the study and evaluated by a Monitoring Committee.

This Supervisory Committee will consist of 3 independent members.

Each member will be required to sign an attestation of no potential pecuniary conflict of interest related to the study results, and should not be known to have a "strong opinion" on the relative merits of the interventions tested in the study.

This Committee will meet at the request of the Scientific Committee, the Sponsor or the investigators.

He will be responsible for:

- Conduct regular reviews of the safety and performance elements of the study to ensure the safety of participants and that the benefit/risk ratio remains favorable for continuation of the trial
- Monitor medical or scientific information made public that may have an impact on the study in progress and the safety of participants
- Carry out the adjudication of the SAEs to decide on the imputability or not of the medical device and/or the procedure of use
- Write recommendations on continuation, modification or discontinuation of the study to the Scientific Committee and the Sponsor, based on the criteria below.

A study termination is considered if:

- The data show a statistically significant increase in the risk of adverse events making the benefit/risk ratio unacceptable,
- A serious and unexpected risk is detected,
- The state of the art makes the studied technology obsolete.

14 ETHICAL AND LEGAL CONSIDERATIONS

14.1 REGULATORY FRAMEWORK OF THE STUDY

This study will be conducted in compliance with the ethical principles of the Declaration of Helsinki revised in 2013, of the ICH-GCP E6(R2) Good Clinical Practices, the ISO 14155 standard, the European Regulation on medical devices 2017/745 and the French legislation on clinical studies .

According to the current French legislation, this study is considered as a type II research involving the human being (RIPH) (interventional study with minimal risks and constraints concerning a CE marked medical device not marketed in France).

14.2 SUBMISSION OF THE PROTOCOL AND STUDY CONTRACT

The study will start only after a favorable opinion of the Committee of Protection of the Persons drawn and will be sent for information to the ANSM.

14.2.1 Declaration to the Competent Regulatory Authorities

The study was registered in the French database and in the European database of studies under the ID-RCB: 2019-A02566-51.

This protocol was sent for information to the French National Agency for the Safety of Medicines and Health Products (ANSM).

Any amendment (corresponding to substantial modifications) will be sent for information to the Competent Authority before its implementation.

Any amendments to the protocol should be sent in writing to all investigators and signed and dated by the sponsor and investigators.

14.2.2 Declaration to the Ethics Committee

The protocol has been submitted in France to the Comité de Protection des Personnes (CPP) SUD-EST VI.

Neither the investigator nor the sponsor may modify this protocol without prior written agreement between the two parties. Any modification considered significant by the investigator or the person in charge of the study must be approved by the CPP before its implementation.

14.2.3 Protection of personal data

The study will be carried out in compliance with the European General Data Protection Regulation (RGPD) and with the French legislation (CNIL).

14.2.4 Declaration to the Orders Professional

The study will be in compliance with the obligations of the profession, and will respect the obligations of transparency of links of interest.

Patient and physician data will be collected in accordance with Chapter IX of Law 78-17 of January 6, 1978, as amended by Law 2004-801 of August 6, 2004 (known as the "Loi Informatique et Libertés") and Article 16 of Law 2018-493 of June 20, 2018 on the protection of personal data.

This protocol of Research Involving the Human Person will be carried out in accordance with the methodology of reference MR-001 of the CNIL of July 21, 2016 (Commission Nationale Informatique et Libertés).

A compliance file to MR-001 was created in order to document the applicable framework of the study. The Sponsor has taken the necessary steps with the CNIL and has committed to respecting the reference methodologies.

14.3 PATIENT INFORMATION AND CONSENT

Patients from whom personal data are collected will be individually informed by the investigating physicians before the beginning of the study (i.e. before any examination that may be necessary to select them for the study) of the objectives of the study, the methods, the nature of the information collected, the purpose of the data processing, the potential benefits and risks related to their participation, and the right to access and rectify the data with the physician.

This information is clearly and legibly stated on an information and consent form. The investigator will provide the patient with a copy of the information and informed consent form. Each patient will be given the opportunity to ask any questions they may have and will be informed of their right to withdraw their consent at any time during the study without having to provide a reason and without any consequences for future care.

Following this informative discussion, the investigator will ask the patient to date and sign the consent form. The patient can only be included in the study by the investigator after having obtained his or her informed, voluntary and written consent.

Any changes to the patient information and consent form must be submitted to the PPC for approval prior to use.

A copy of the dated and signed consent form should be given to the patient. The investigator should retain the original signed and dated consent form in the study file. The investigator will indicate on each case report form that he/she has informed the patient of the study and has obtained his/her voluntary written consent.

14.4 PRIVACY

All study materials provided by the Sponsor to the Investigator and his or her designated personnel are subject to a duty of confidentiality. Under no circumstances should their contents be disclosed to any third party not directly involved in the study, without the prior written permission of the Sponsor.

The investigator must ensure that patient anonymity is maintained. A unique identification code will be associated with each patient and used in all communications.

